2 ELIGIBILITY ASSESSMENT AND ENROLLMENT

Nirogacestat will be administered at the recommended Phase II dose of 150 mg BID orally, continually, in 21-day cycles. Optional tumor biopsies for research purposes will be performed at baseline prior to study treatment and at the beginning of cycle 7 (+/- one cycle).

2.1 ELIGIBILITY CRITERIA

2.1.1 Inclusion Criteria

- 2.1.1.1 Patients must have histologically confirmed desmoid tumor confirmed by the Laboratory of Pathology, NCI, that has progressed after receiving at least one line of standard treatment and that is not amenable to surgical resection or definitive radiation therapy.
- 2.1.1.2 Willingness to provide blood samples and 10 unstained slides or a tumor block for genetic research studies.
- 2.1.1.3 Any line of therapy with prior desmoid therapy, including radiotherapy, should have been completed at least 2 weeks before study entry and all toxicities must have resolved at least to eligibility levels.
- 2.1.1.4 Age ≥18 years; because no dosing or adverse event data are currently available on the use of Nirogacestat in patients <18 years of age, children are excluded from this study, but may be eligible for future pediatric trials.
- 2.1.1.5 ECOG performance status <2 (see Appendix A).
- 2.1.1.6 Life expectancy > 3 months.
- 2.1.1.7 Patients must have normal organ and marrow function as defined below:

absolute neutrophil count $\geq 1,500/\text{mcL}$ platelets $\geq 100,000/\text{mcL}$

total bilirubin $\leq 1.5 \text{ X}$ institutional upper limit of normal AST(SGOT)/ALT(SGPT) $\leq 5 \text{ X}$ institutional upper limit of normal

creatinine < 1.5 X institutional upper limit of normal

OR

creatinine clearance $\geq 60 \text{ mL/min/1.73 m}^2 \text{ for patients with}$

creatinine levels >1.5 mg/dL

hemoglobin $\geq 9 \text{ g/dL}$

2.1.1.8 Patients must be able to swallow whole tablets or capsules with no GI condition affecting absorption; nasogastric or G-tube administration is not allowed.

- 2.1.1.9 The effects of Nirogacestat on the developing human fetus are unknown. For this reason and because γ-secretase inhibitors are known to be teratogenic, women of child-bearing potential and men must agree to use adequate contraception (hormonal or barrier method of birth control; abstinence) for the duration of study participation and for at least 6 months after dosing with study drugs ceases. Should a woman become pregnant or suspect she is pregnant while she or her partner is participating in this study, she should inform her treating physician immediately. Men treated or enrolled on this protocol must also agree to use adequate contraception for the duration of study participation, and 6 months after completion of study drug administration.
- 2.1.1.10 Ability to understand and the willingness to sign a written informed consent document.
- 2.1.1.11 Evidence of measurable disease by CT scan. Measurable lesions are defined as those that can be accurately measured in at least one dimension (longest diameter to be recorded) as ≥20 mm by chest x-ray, as ≥10 mm with CT scan, or ≥10 mm with calipers by clinical exam.

2.1.2 Exclusion Criteria

- 2.1.2.1 Patients who are receiving any other investigational agents. Concurrent mediations that the patient is taking will be reviewed by the PI to assess safety and eligibility.
- 2.1.2.2 Prior treatment with γ -secretase inhibitors or anti-notch antibody therapy.
- 2.1.2.3 Uncontrolled intercurrent illness including, but not limited to, serious infection, symptomatic congestive heart failure, unstable angina pectoris, cardiac arrhythmia, or psychiatric illness/social situations that would limit compliance with study requirements.
- 2.1.2.4 QTc interval of >470 msec at study entry; congenital long QT syndrome.
- 2.1.2.5 Pregnant women are excluded from this study because Nirogacestat is a γ-secretase inhibitor with the potential for teratogenic or abortifacient effects. Because there is an unknown but potential risk for adverse events in nursing infants secondary to treatment of the mother with Nirogacestat, breastfeeding should be discontinued if the mother is treated with Nirogacestat.
- 2.1.2.6 Patients with gastrointestinal conditions that might predispose for drug intolerability or poor drug absorption (e.g., inability to take oral medication or a requirement for IV alimentation, prior surgical procedures affecting absorption, malabsorption syndrome, and active peptic ulcer disease) are excluded. Subjects with ulcerative colitis,

inflammatory bowel disease, or a partial or complete small bowel obstruction are also excluded, as are any patients who cannot swallow the tablet whole. Tablets must not be crushed or chewed; nasogastric or G-tube administration is not allowed.

2.1.2.7 HIV-positive patients on combination antiretroviral therapy are ineligible because of the potential for pharmacokinetic interactions with Nirogacestat.

2.1.3 Recruitment Strategies

We have had multiple discussions with the Desmoid Tumor Research Foundation, Inc., who have various outreach efforts including patient meetings and webcasts. Senior executives of the Foundation have indicated strong interest in this trial and willingness to inform their members. We also have a network of referring physicians nationally that refers patients with solid tumors to our clinical program. Given our interest and trials for sarcomas, we have formed connections with centers that treat patients with mesenchymal malignancies. We will be informing all of these of the availability of this trial once it is open.

2.2 SCREENING EVALUATION

- 2.2.1.1 Histologic confirmation: A block or stained slides of tumor tissue from each participant to confirm diagnosis. All patients will be required to submit a tumor block or 10 unstained slides for genetic research purposes.
- 2.2.1.2 History and physical examination: Complete history and physical examination (including height, weight, vital signs, performance score, EKG) will be conducted within 72 hours prior to enrollment.
- 2.2.1.3 Imaging Studies (Baseline): Every participant should have an evaluation of known sites of disease as part of the baseline evaluation. All patients will be required to undergo a CT scan of the area of known disease; an MRI with diffusion weighting may be performed prior to start of study treatment, at the end of cycle 1, and at the time of restaging, per PI's discretion.
- 2.2.1.4 Laboratory Evaluation: Baseline laboratory data are to be obtained within 72 hours prior to enrollment:
 - Hematological Profile: CBC with differential.
 - Biochemical Profile: albumin, alkaline phosphatase, total bilirubin, BUN, calcium, creatinine, phosphorus, SGOT[AST], SGPT[ALT], magnesium, potassium, and sodium.
 - Coagulation Profile: PT, PTT, INR
 - Urine and/or serum pregnancy test for female participants of childbearing potential.

2.3 REGISTRATION PROCEDURES

Authorized staff must register an eligible candidate with NCI Central Registration Office (CRO) within 24 hours of signing consent. A registration Eligibility Checklist from the Web site (http://home.ccr.cancer.gov/intra/eligibility/welcome.htm) must be completed and sent via encrypted email to: NCI Central Registration Office [contact].

After confirmation of eligibility at Central Registration Office, CRO staff will call pharmacy to advise them of the acceptance of the patient on the protocol prior to the release of investigational agent. Verification of Registration will be forwarded electronically via e-mail to the research team. A recorder is available during non-working hours.

Off Protocol Therapy and Off-Study Procedure: Authorized staff must notify the Central Registration Office (CRO) when a patient is taken off protocol therapy and when a patient is taken off-study. The Participant Status Updates Form from the Web site (http://home.ccr.cancer.gov/intra/eligibility/welcome.htm) main page must be completed and sent via encrypted email to the NCI Central Registration Office (HOIS; [contact]).

2.4 RANDOMIZATION PROCEDURES

N/A

3 STUDY IMPLEMENTATION

3.1 STUDY DESIGN

This is an open-label Phase II trial of Nirogacestat. Study drug will be administered at 150 mg, orally, BID, continually, in 21-day cycles.

Labs (CBC with differential and serum chemistries, including electrolytes) will be monitored each week during cycle 1, and then every other cycle. History and physical examination will be performed before the start of every other cycle. For patients having a history and physical examination performed by their local physician, study drug will be held until receipt of results; this may result in an interruption of therapy. For patients on study for more than a year, history and physical examination and labs can be performed every 3 cycles (up to 2 weeks before the start of the cycle). EKG monitoring will be performed at baseline and then post-drug administration on study day 1. Additional EKG monitoring may be performed during cycle 1 as clinically indicated.

Response assessment will be performed using RECIST 1.1. Restaging scans (CT scans of the known site of disease) will be performed at baseline prior to starting study treatment and then every 6 cycles (+/- 1 cycle) as described in Section 5.5. An MRI with diffusion weighting may be performed prior to start of study treatment, end of cycle 1, and at the time of restaging, per PI's discretion.

Health-related quality of life (HRQOL)/symptom questionnaires will be administered at baseline and at restaging (response assessment) as described in Section 3.4.

Archival unstained slides or tumor block will be sent for genetic research studies as described in Section 5.4.

Blood for research (whole exome sequencing) will be collected at baseline as described in Section 5.2.

Optional tumor biopsies for research purposes will be performed at baseline prior to study treatment and at the beginning of cycle 7 (+/- one cycle) as described in Section 5.2.

3.2 DRUG ADMINISTRATION

Reported adverse events and potential risks are described in Section 11.1. Appropriate dose modifications are described in Section 3.3. No investigational or commercial agents or therapies other than those described below may be administered with the intent to treat the patient's tumor.

Patients will be asked to maintain a Study Medication Diary (Appendix B) and record each dose of medication. Patients will be given instructions for completing the medication diary and will be asked to return it to the clinic staff at their follow up visits. There is no restriction on taking the study drug with food; patients who miss a dose or vomit the drug will be instructed to not take an additional dose. A cycle will be considered completed if 90% of the planned dose is administered. Occasionally patients may miss a dose for non-medical reasons, but this should not have an impact in the overall conduct of the trial or be a risk to their safety.

3.3 DOSE MODIFICATIONS

- Grade 3 non-hematologic toxicities (other than alopecia; easily correctable electrolyte abnormalities) would require holding study drug until recovery to grade ≤ 2 or baseline, with reinstituting study drug at the next lower dose level (see below).
- Grade 2 or higher nausea, vomiting, or diarrhea would result in dose reduction only if not controlled by supportive measures.
- Any grade of allergic reaction would result in discontinuing study drug and taking patient off study.
- Grade 3 hematologic toxicities (except any grade lymphopenia, leucopenia in the absence of neutropenia) would result in dose being held till recovery to grade 2 or less with reinstitution of study drug at the next lower dose level. Anemia would require dose reduction if there is a drop in hemoglobin of ≥ 2 g/dL from baseline without other causes such as nutritional deficiency.

A maximum of 2 dose reductions will be allowed on study. Study drug can be held for a maximum of 3 weeks to allow recovery from toxicities. If toxicities do not resolve to retreatment criteria by the end of 3 weeks, the patient will only resume treatment at the discretion of the PI (i.e., if the patient is benefiting from therapy).

Dose Level	Dose (orally BID q 21-day cycles)				
-1	100 mg				

Version Date: 5-18-2023

2	80 ··· ~
-2	80 mg

3.4 PATIENT REPORTED OUTCOME QUESTIONNAIRE

Participants on this study will be asked to complete health-related quality-of-life (HRQOL)/symptom questionnaires to assess the severity and associated interference caused by disease and treatment-related symptoms and track their severity and interference over the course of treatment. These patient-reported outcome (PRO) measures will capture the emergence or worsening of selected symptoms from baseline to study completion, thus improving the identification of treatment-emergent symptomatic toxicity and better capturing improvements in disease-related symptoms which may inform decisions about therapeutic response and clinical benefit Such patient-reported outcomes (PRO) allow participants to rate their own HRQOL, thereby providing a direct measure of each patient's experience of treatment over the course of the study [26, 27].

This protocol will use the psychometrically-validated M.D. Anderson Symptom Inventory (MDASI) to assess PRO disease and treatment-related symptoms [28]. MDASI uses a 0-10 numerical scale to assess, over the previous 24 hours, 13 symptoms commonly experienced by patients with cancer and 6 additional items that assess the extent to which these symptoms interfered with how patients felt and were able to function:

- 13 treatment symptoms assessed: pain, fatigue, nausea, disturbed sleep, distress (emotional), shortness of breath, lack of appetite, drowsiness, dry mouth, sadness, vomiting, difficulty remembering, and numbness or tingling
- 6 symptom interference items assessed: general activity, mood, walking ability, normal work, relations with other people, and enjoyment of life

A copy of MDASI is provided in Appendix D. The questionnaires will be administered at baseline and at restaging. Completing the MDASI takes approximately 2-5 minutes and the symptom scale will take an additional 5 minutes to complete. All patients will complete these questionnaires under the supervision of a member of the clinic staff.

A component score representing symptom severity is obtained by taking the average of the 13 symptom items together. A component score representing symptom distress is obtaining by averaging the 6 symptom interference items. Questionnaires will be maintained in the research chart of each patient. The NCI has received permission to use MDASI by the copyright holder, The University of Texas MD Anderson Cancer Center.

3.5 STUDY CALENDAR

Baseline history and physical exam are to be conducted within 1 week prior to start of protocol therapy; laboratory evaluations must be done within 72 hours prior to start of protocol therapy. Scans and x-rays must be done ≤ 28 days prior to the start of therapy. The duration of a cycle will be 21 days (\pm 1 day for scheduling). The start of the next cycle may be delayed for up to 1 week to accommodate scheduling conflicts. History and physical examination and laboratory

Version Date: 5-18-2023

evaluations can be performed before the start of a cycle. For patients having their history and physical examination performed by their local physician, study drug will be held until receipt of results. For patients on study for more than a year, history, physical examination, and labs can be performed every 3 cycles (up to 2 weeks before the start of the cycle).

Version Date: 5-18-2023

	Pre- Study	C1 W1 (D1-7)	C1 W2 (D8-14)	C1 W3 D15-21)	C2 W1 (D1-7)	C2 W2 (D8-14)	C2 W3 (D15-21)	C3 W1 on	Off Treat- ment
Nirogacestat (PF- 03084014) ^a		X	X	X	X	X	X	X	
Informed consent	X								
Demographics	X								
Medical history	X								
Concurrent meds	X	X						X	
Physical exam ^b	X							X	X
Vital signs ^b	X							X	X
Height	X								
Weight b	X							X	X
Performance status ^b	X							X	X
CBC w/diff, plts ^c	X		X	X				X	X
Serum chemistry ^c	X		X	X				X	X
Coagulation profile	X								
Adverse event evaluation		X						X	X
Tumor measurements d	X								X
B-HCG ^e	X								
EKG ^f	X								
Tumor biopsies g	X								
Archival tissue h									
PG blood sampling h	X								
Questionnaire i	X								

- a. PF-03084014 twice daily in 21-day cycles.
- b. Should be performed on day 1 at the Clinical Center, and then at the start of every other cycle at the Clinical Center or by patient's local physician. For patients on study more than a year, history and physical examination can be performed every 3 cycles (up to 2 weeks before the start of the cycle).
- c. Serum chemistry (albumin, alkaline phosphatase, total bilirubin, BUN, calcium, creatinine, glucose, phosphorus, magnesium, potassium, SGOT [AST], SGPT [ALT], sodium) and CBC w/diff, platelets should be performed within 72 hours before enrollment (pre-study) and weekly during cycle 1, at the start of every other cycle and as clinically indicated. For patients on study more than a year, labs can be performed every 3 cycles (up to 2 weeks before the start of the cycle).
- d. Tumor measurements are repeated every 6 cycles (±1 cycle). Documentation (radiologic) must be provided for patients removed from study for progressive disease. Optional MRI scans may be performed prior to start of study treatment, end of cycle 1, and every 6 cycles.
- e. Serum or urine pregnancy test (women of childbearing potential) within 1 week prior to enrollment

- f. EKG at baseline and then post-drug administration on day 1. Additional monitoring may be performed during cycle 1 as clinically indicated.
- g. Tumor biopsies are optional at baseline and at the beginning of cycle 7
- h. Archival tumor biopsy tissue and blood sample for pharmacogenomic analysis collected at baseline
- i. Quality-of-life questionnaire to be administered at baseline and at restaging

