4 CONCOMITANT MEDICATIONS

All patients will be provided with the best available supportive care. All concurrent medications should be documented prior to initiation of treatment, and be periodically reviewed with the patient. Particular attention must be paid to medications which may cause hemolytic anemia.

No other approved or investigational treatment for desmoid tumors will be permitted during the study period, including chemotherapy, biologic response modifiers, hormone therapy, immunotherapy, or radiotherapy.

Nausea/Vomiting

Anti-emetics will not be administered routinely prior to Nirogacestat. However, if a patient develops nausea/vomiting, anti-emetics such as but not limited to prochlorperazine, metoclopramide, 5-HT3 antagonists, or aprepitant may be given. In addition, if a patient develops nausea and/or vomiting that is Grade 2 or greater, anti-emetics may be instituted prophylactically at the discretion of the investigator. Nausea and vomiting will be considered refractory if it does not resolve to \leq Grade 1 with treatment with a combination of at least 2 of the antiemetics within 24 hours.

Diarrhea

If diarrhea develops and does not have an identifiable cause other than study drug administration, anti-diarrheals such as Lomotil (diphenoxylate HCl 2.5 mg + atropine sulfate 0.025 mg/tablet) dosed according to package insert or loperamide 4 mg po after the first unformed stool with 2 mg po every 2 hours as long as unformed stools continue (4 mg every 4 hours while asleep). No more than 16 mg of loperamide should be taken during a 24-hour period. This regimen can be repeated for each diarrheal episode. Diarrhea will be considered refractory if it does not resolve within 24 hours to Grade \leq 2 with the above regimen ((loperamide \leq 16 mg in a 24-hour period if there is resolution of the symptoms).

Neutropenia

Febrile neutropenia is a life-threatening complication requiring hospitalization and urgent broad-spectrum antibiotics, as well as an aggressive search for the source and microbial cause of the episode. Growth factors to prevent neutropenia will not be administered prophylactically. If necessary, they may be administered according to accepted American Society of Clinical Oncology (ASCO) guidelines to allow re-treatment.

Anemia

Symptomatic anemia should be treated with red blood cell transfusion and is recommended if the hemoglobin falls below 8 g/dL. Use of erythropoietin will follow ASCO guidelines.

Thrombocytopenia

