6.2.3 Methods for Evaluation of Measurable Disease

All measurements should be taken and recorded in metric notation using a ruler or calipers. All baseline evaluations should be performed as closely as possible to the beginning of treatment and never more than 4 weeks before the beginning of the treatment.

The same method of assessment and the same technique should be used to characterize each identified and reported lesion at baseline and during follow-up. Imaging-based evaluation is preferred to evaluation by clinical examination unless the lesion(s) being followed cannot be imaged but are assessable by clinical exam.

Clinical lesions: Clinical lesions will only be considered measurable when they are superficial (e.g., skin nodules and palpable lymph nodes) and ≥10 mm diameter as assessed using calipers (e.g., skin nodules). In the case of skin lesions, documentation by color photography, including a ruler to estimate the size of the lesion, is recommended.

Chest x-ray: Lesions on chest x-ray are acceptable as measurable lesions when they are clearly defined and surrounded by aerated lung. However, CT is preferable.

Conventional CT and MRI: This guideline has defined measurability of lesions on CT scan based on the assumption that CT slice thickness is 5 mm or less. If CT scans have slice thickness greater than 5 mm, the minimum size for a measurable lesion should be twice the slice thickness. MRI is also acceptable in certain situations (e.g. for body scans).

Use of MRI remains a complex issue. MRI has excellent contrast, spatial, and temporal resolution; however, there are many image acquisition variables involved in MRI, which greatly impact image quality, lesion conspicuity, and measurement. Furthermore, the availability of MRI is variable globally. As with CT, if an MRI is performed, the technical specifications of the scanning sequences used should be optimized for the evaluation of the type and site of disease. Furthermore, as with CT, the modality used at follow-up should be the same as was used at baseline and the lesions should be measured/assessed on the same pulse sequence. It is beyond the scope of the RECIST guidelines to prescribe specific MRI pulse sequence parameters for all

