6.2.4 Response Criteria

6.2.4.1 Evaluation of Target Lesions

Complete Response (CR): Disappearance of all target lesions. Any pathological lymph nodes (whether target or non-target) must have reduction in short axis to <10 mm.

Partial Response (PR): At least a 30% decrease in the sum of the diameters of target lesions, taking as reference the baseline sum diameters.

Progressive Disease (PD): At least a 20% increase in the sum of the diameters of target lesions, taking as reference the smallest sum on study (this includes the baseline sum if that is the smallest on study). In addition to the relative increase of 20%, the sum must also demonstrate an absolute increase of at least 5 mm. (Note: the appearance of one or more new lesions is also considered progressions).

Stable Disease (SD): Neither sufficient shrinkage to qualify for PR nor sufficient increase to qualify for PD, taking as reference the smallest sum diameters while on study.

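### Does the baseline CT need to be tied to the end of prior desmoid therapy?

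*Combined protocol and SAP*

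**What the plan says.** Two windows bear on the reference scan, and they start from different dates.

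- **CT window.** Section 3.5: "Scans and x-rays must be done ≤ 28 days prior to the start of therapy". Section 6.2.3 repeats the limit and states a preference for late scans: baseline evaluations are to be "performed as closely as possible to the beginning of treatment and never more than 4 weeks before the beginning of the treatment". Section 2.2.1.3 makes the scan compulsory: "All patients will be required to undergo a CT scan of the area of known disease". Section 3.1 orders it against study drug only: restaging scans "will be performed at baseline prior to starting study treatment".
- **Washout.** Section 2.1.1.3 says that prior desmoid therapy, radiotherapy included, "should have been completed at least 2 weeks before study entry". Section 2.1.1.1 requires a tumour "that has progressed after receiving at least one line of standard treatment", which need not be the latest line. Section 4 adds: "No other approved or investigational treatment for desmoid tumors will be permitted during the study period".

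The baseline scan defines the endpoint. Under Section 6.2.4.1, partial response is "At least a 30% decrease in the sum of the diameters of target lesions, taking as reference the baseline sum diameters". Section 10 rejects a 10% response rate if at least 4 of 17 patients respond.

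**The concern.** The CT window runs back from first dose and the washout runs back from study entry. A scan near the start of its window can therefore fall before a prior therapy that stopped only just in time. The reference sum of diameters would then have been measured while the patient was still on the earlier treatment.

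There is no control arm to absorb the difference. If the tumour shrank between that scan and the end of the earlier therapy, part of the 30% decrease would be credited to nirogacestat without being its effect. If it grew, a true response would be harder to reach. With a cut-off of 4 responders in 17, one misclassified patient can decide the trial when the count stands at 3 or 4.

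**Working it through.** **Longest possible overlap.** Take first dose as day 0 and let g be the days from study entry to first dose.

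- Earliest CT (Sections 3.5 and 6.2.3): day -28.
- Latest permitted end of prior therapy (Section 2.1.1.3): day -(14 + g).
- Longest lead of the CT over the end of therapy: 28 - 14 - g = 14 - g days.

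| g (days) | 0 | 1 | 3 | 7 | 10 | 14 |
|---|---|---|---|---|---|---|
| Longest lead (days) | 14 | 13 | 11 | 7 | 4 | 0 |

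The protocol does not state g. Section 2.2.1.4 ties baseline laboratory tests to 72 hours before enrolment, and Section 3.5 ties them to 72 hours before therapy. If one blood draw serves both, g is about 0 to 3 days (assumption). A baseline biopsy, which Section 5.2.2.2 places after enrolment, could lengthen it.

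**What has to happen for any overlap.** The CT must fall between 15 + g and 28 days before first dose. Section 2.3 requires registration within 24 hours of consent, and Section 12.5 puts consent before entry. If entry means registration, a CT done after consent falls at the earliest 1 day before entry, so at least 14 - 1 = 13 days after prior therapy ended. An overlap therefore needs an earlier scan reused as baseline, against the Section 6.2.3 preference for a late one.

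There are two routes:

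- The latest line was stopped without progression. Shrinkage after the scan would favour nirogacestat.
- A CT showing progression on the latest line is reused as baseline. Further growth would count against nirogacestat.

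**Effect on the response threshold.** Let d be the fractional shrinkage between the CT and the end of prior therapy (negative for growth). Measured from tumour size at the end of that therapy, the decrease needed for a partial response is 1 - 0.70/(1 - d). The values of d are assumed.

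| Change during overlap | 1% | 3% | 5% |
|---|---|---|---|
| Shrinkage: decrease needed | 29.3% | 27.8% | 26.3% |
| Growth: decrease needed | 30.7% | 32.0% | 33.3% |

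For scale, the first restaging comes at about 6 x 21 = 126 days, and Section 1.2.1 describes these tumours as slow-growing.

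**Effect on the decision rule.** The plan's own rule first, by exact binomial:

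- Type I error: P(X >= 4 | n = 17, p = 0.10) = 0.0826, within the planned 0.10.
- Power: P(X >= 4 | n = 17, p = 0.35) = 0.8972, against the stated 0.90.

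Now let k patients be exposed. For type I error, each has an added chance a of a false response, so the response probability is p_e = 0.10 + 0.90a. For power, each loses b, so p_e = 0.35 - b. The other 17 - k patients keep p = 0.10 or 0.35. The rejection probability is the sum over i = 0 to k of Bin(i; k, p_e) x P(X >= 4 - i | 17 - k, p). All values of k, a and b are assumed.

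| k | Type I error, a = 1% | Type I error, a = 5% | Power, b = 0.01 | Power, b = 0.05 |
|---|---|---|---|---|
| 1 | 0.0839 | 0.0890 | 0.8963 | 0.8928 |
| 2 | 0.0852 | 0.0957 | 0.8954 | 0.8882 |

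Type I error reaches 0.10 only at a = 13.6% with one exposed patient, or 6.6% with two.

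**What a scan-order rule would change.** Suppose the CT had to follow the last dose or fraction.

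- Therapy ends day -29, CT on day -28: the rule is met, and 28 days of delayed effect can still fall between the reference scan and first dose.
- Therapy ends day -27, CT on day -28: the rule is broken by one day.

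The carry-over in the two cases is practically the same.

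**The case for a change.** The strongest argument for a change is that the gap is real and cheap to close. No section available for review sets the order, the preference in Section 6.2.3 is not a rule, and nothing requires the CT to follow consent, so a scan from before consent can be reused. The CT is already compulsory, so one sentence would settle the order without touching the washout, the 17 patients or the cut-off. Because the rule turns on a single responder, even a rare misclassification could matter.

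The textual point stands. What does not follow is a gain. The main carry-over route is the delayed effect of therapy that ended before the CT, radiotherapy for example, and a rule on order leaves it open. The cost is small but not nil. Section 2.1.3 describes national referral, so some patients may arrive already scanned elsewhere. Repeating such a CT adds radiation to the exposure of up to about 6 rem per year in Section 12.4, which that section already places above a guideline of less than 5.0 rem.

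**Conclusion.** No change is needed. The windows permit a lead of at most 14 - g days, but as a ceiling. It needs a reused scan from before consent, therapy stopped at the edge of the washout, and entry close to first dose. The bias can run in either direction, and the route through a progression scan runs against the drug.

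The documents give no count of affected patients and no tumour change over such an interval, so the operating figures only illustrate the scale. With one or two patients exposed and a shift of 1 to 5 percentage points, type I error stays at or below 0.096 against the planned 0.10, and power at or above 0.888 against 0.897. The margin is not unlimited: two exposed patients with an added chance above about 7% would pass 0.10, but nothing in the documents points to that.

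This is a detail that analysts can handle with information they must already have. Checking the washout requires the end date of prior therapy, and checking the 28-day limit requires the CT date, so any patient scanned too early can be identified and described when results are reported.
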